## **CHAPTER 4 RECRUITMENT AND DATA COLLECTION**

### 4.1 Recruitment Overview

Participants will be recruited from the Boston area community, including senior housing facilities in urban/suburban areas and research recruitment repositories. We will utilize a multi-pronged approach to meet our recruitment goals:

- We will recruit from the research repository that resides at HRC
- We will connect with social workers in and outside the HRC
- We will perform medical record reviews to identify potentially eligible individuals at the Hebrew SeniorLife (HSL) geriatric medicine practices.
- We will advertise through direct mailings to all residents of HRC's seven supportive housing facilities (over 3,000 residents).
- We will give presentations at each Hebrew SeniorLife (HSL) facility.
- We will use the Harvard Catalyst (CTSA) Shared Health Research Information Network (SHRINE) to identify volunteers from Harvard-affiliated hospitals and clinics.
- We will advertise our study within numerous local media outlets, on HRC's Hinda and Arthur Marcus Institute for Aging Research and other websites (e.g., Craig's List), and at [www.clinicaltrials.gov](http://www.clinicaltrials.gov).

## 4.2 Recruitment Timeline

Our trial proposes to enroll 40 persons over approximately 6-months. We will recruit for two waves of our intervention. For the first wave of the intervention, we aim to recruit 16 individuals over ~3 months. The 16 individuals will then be randomized to the intervention or control group, and participate in the study for 3 months. During the 3 months the first wave of participants are on the study intervention, we will be recruiting for the second wave (n=24) of the intervention. Once the second cohort of 24 individuals is recruited, they will begin the study intervention as soon as possible. To stay on target, we need to recruit ~7 participants/month. Thus, based on our known research participation rates, and the expected prevalence of depressive symptoms in older adults, we will readily be able to meet our recruitment goal of 40 participants.

There will be two waves of the intervention (n=16 for the first wave, and n=24 for the second wave). For each wave, half of the participants will be randomized to the intervention group and the other half will be in the control group. In an attempt to account for the impact of seasonal variation on physical activity levels, we will employ block (blocks of 4) randomization. For every block of 4 participants, 2 will be randomized to consume the placebo powder and the remaining 2 will be randomized to the blueberry powder.

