#### Inclusion Criteria

- Men and women aged  $\geq 65$  years
- Self-reporting  $\geq 8$  hours of sitting per/day (e.g., sedentary behavior)
- Depressive symptoms (defined as  $\geq 4$  and  $< 16$  points on the center for epidemiological studies depression-scale)

Exclusion criteria have been selected to ensure safety and optimize compliance, while minimizing confounds due to overt disease or conditions that may significantly influence study outcomes. Given that this is pilot a study, select criteria will be per discretion of the principal investigator. Exclusions may be during the telephone or in-person screening as described below:

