### 3.6 Study Intervention Products

Given that 100% purified anthocyanins are not commercially available, we will utilize a dietary source of anthocyanins. Blueberries are one of the richest sources of dietary anthocyanins and also conveniently concentrated with fiber. To allow for blinding, we will use freeze-dried powdered blueberries as our intervention product. The powder will be provided by the U.S. Blueberry Council. The placebo powder will also be provided by the U.S. Blueberry Council, which is a nutritionally matched powder except it contains minimal amounts of anthocyanins and fiber. The placebo powder will be labeled with either a letter or number that is different from the intervention powder. This is a double-blind intervention, so neither the participants nor the study staff will know which powder is the placebo and/or which is the blueberry powder. See §5.3 for further information on dietary intervention.

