Objective Measure of Sedentary Behavior will be measured as a final assessment of eligibility. All participants that pass the in-person screen up to this point will be provided an accelerometer (ActiGraph, GT9X Link), which is a research-grade activity tracker that monitors several aspects of activity, including step counts. They will be instructed to wear the device during the week to use as an objective assessment of their sedentary behavior, specifically their usual daily step count. After a week of wearing the activity monitor, the participant’s ActiGraph will be synched in order to calculate their median daily step count over the past week. Individuals that have a median step count >7,500 steps per day will be excluded. All eligible participants will be asked to continue to wear the ActiGraph for the remainder of the study.

To ensure participants have a stable level of dietary influence on inflammation, all participants will be asked to avoid consumption of certain foods (e.g., fiber-rich and anthocyanin-rich foods; i.e., washout period). Additionally, the week before baseline participants will be asked to fill a 3-day diet record to estimate nutrient intake.

**Baseline Visit (~60 minutes):** At the baseline visit, participants will be asked to turn in their 3-day diet records and sync their ActiGraph devices to transfer their activity data and evaluate engagement in physical activity. Height, weight, vitals, suicidal ideation (P4SS), depressive level (PHQ-9), social network, motivation, and relevant symptoms will be evaluated. Additionally, up to 10 mL of blood will be taken to measure inflammation-related markers in serum. Finally, a personalized daily step goal will be calculated for each participant. Utilizing the step count data assessed during the 2-week washout, the 20% increase of his/her median usual daily steps measured will be calculated and be defined as a personalized step-goal. Study staff will share this personalized step goal with the participant and say, “this is the recommended number of steps you should try to meet each day during the study.” Participants will be given their allotment of powder to consume.

**Social Network:** Subjective perception of social support and connectedness will be evaluated using a validated questionnaire.

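### Disclosed fixed blocks of 4, one label code per arm and no described concealment make about a third of upcoming codes deducible if participants are assigned one at a time

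*Combined protocol and SAP*

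**What the plan says.** Section 4.2 plans two waves: "There will be two waves of the intervention (n=16 for the first wave, and n=24 for the second wave", with half of each wave in each arm. It gives seasonal variation in activity as the reason why "we will employ block (blocks of 4) randomization", and fixes the split: "For every block of 4 participants, 2 will be randomized to consume the placebo powder", which leaves two blueberry places in each block.

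On labelling, section 3.6 says "The placebo powder will be labeled with either a letter or number that is different from the intervention powder". This reads as two codes in all, one per arm. The same section says "neither the participants nor the study staff will know which powder is the placebo and/or which is the blueberry powder", and section 4.6 repeats that staff and participants are blinded.

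At the baseline visit in section 5.2, "Participants will be given their allotment of powder to consume", and used and unused packets come back at later visits for the compliance count. Section 3.3 says "select criteria will be per discretion of the principal investigator".

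The document does not say who generates or holds the sequence, or how the next assignment is kept from those who enrol. Nor is it consistent on timing. Section 4.2 has the 16 of wave 1 recruited and then randomised, and has wave 2 begin once its 24 are recruited. Sections 3.2, 5.2 and 5.3 describe the path of one person: screening, a two-week run-in, baseline assessments, randomisation and powder.

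**The concern.** Blinding to what a powder contains and concealment of the next assignment are separate protections. Sections 3.6 and 4.6 deal with the first; nothing deals with the second. A block whose size is constant and published, combined with a code common to everyone in an arm, lets an observer count. Once two packets of one code have gone out in a block, the rest of that block is known.

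Section 6.3 compares mean change in steps with a t-test that has no baseline adjustment, planned at 20 per group. If people expected to become more active were placed on one code, the analysis would not correct for it. Some discretion exists: several exclusions in section 3.3, including the step-count limit, may be varied by the PI, and section 4.4 lets a person withdrawn before starting begin again in some circumstances.

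The seasonal reason does not clearly require the blocks. If a wave is randomised as a batch, halving it already balances the arms by season. If assignment is staggered, entry-order blocks do help with calendar time, but that is also the setting in which codes can be predicted.

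**Working it through.** The plan states no predictability figure, so there is none to reproduce.

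**Inputs.** Section 4.2: block size 4, split 2:2; waves of 16 (4 blocks) and 24 (6 blocks). Section 3.6: one code per arm, as read above. Assumed: assignment is sequential, and the observer knows the block size and where blocks start, and has seen all earlier codes.

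**Codes known with certainty, blocks of 4.** There are C(4,2) = 6 equally likely orders.
- The 4th code is always known.
- The 3rd is known when the first two match, probability 2/6 = 1/3.
- Expected number per block = 1 + 1/3 = 4/3, that is 33.3%.
- Over 10 blocks: 10 × 4/3 = 13.3 of 40 (wave 1: 4 × 4/3 = 5.3; wave 2: 6 × 4/3 = 8.0). The possible range is 10 to 20, since each block yields 1 or 2.

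**Best guess, blocks of 4.** The observer names the code in shorter supply so far.
- 1st: right 1/2 of the time. 2nd: 2/3.
- 3rd: 1 if the first two match, otherwise 1/2, so 1/3 + (2/3)(1/2) = 2/3.
- 4th: 1.
- Sum = 2.833 of 4, or 70.8%, against 50% by chance.

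**One permutation per wave.** With m per arm, the expected number certain is 2m/(m+1).
- Wave 1 (m = 8): 16/9 = 1.78. Wave 2 (m = 12): 24/13 = 1.85. Total 3.6 of 40 (9%).
- Correct best guesses: 10.05 of 16 and 14.60 of 24, together 24.65 of 40 = 61.6%.

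**Undisclosed, varied blocks.** By simulation, sizes of 4 and 6 in random order, with the list cut at each wave's size, leave about 2.3 of 40 certain (6%); sizes of 2 and 4 leave about 4.1 (10%).

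**Illustration only; the steering is assumed.** Suppose no true effect, and that staff place people whose expected change differs from average by ±d steps/day according to their best guess, always in the same direction. Bias = d × (correct − incorrect guesses)/20. The type I error comes from the noncentral t with the SD of 1045 in section 6.4, 20 per group and two-sided 0.05.

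| Setting | Factor | d = 100 | d = 250 |
|---|---|---|---|
| Blocks of 4, all 40 steered | (28.33 − 11.67)/20 = 0.833 | 83 steps, 5.7% | 208 steps, 9.4% |
| Blocks of 4, wave 2 only | (17 − 7)/20 = 0.5 | 50 steps, 5.2% | 125 steps, 6.6% |
| Wave list, all 40 steered | (24.65 − 15.35)/20 = 0.465 | 46 steps, 5.2% | 116 steps, 6.4% |

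No passage supports any particular d, or says that steering would occur.

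**The case against.** Four points weigh on the other side.

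1. **Timing.** On the plain reading of section 4.2, eligibility in wave 1 is settled before any code is issued, so no code could influence who is enrolled. That stands for batch assignment; what then remains is the order of people already enrolled. It is not decisive, because sections 3.2, 5.2 and 5.3 fit one-at-a-time assignment at baseline visits of about an hour each, and 4.2 is less explicit for wave 2. The document does not settle it.

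2. **Eligibility precedes allocation.** Exclusions are made at screening, and the step limit is checked after one week of a two-week run-in. The next code at that decision need not be that person's code. This stands, and narrows the risk further towards ordering.

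3. **A code is not a treatment.** Steering towards a code of unknown meaning has no expected direction. This also stands. It is tempered by there being only two codes, so that one correct inference, for example from the gastrointestinal symptoms that section 8.2 says are captured at each visit, would identify a whole arm. Wave 1 experience could inform wave 2 if the codes carry over, which is not stated.

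4. **Who sees the codes.** A reader might infer that the same staff enrol, dispense and collect packets. Sections 5.2 and 5.3 do not say who does these things; it is a fair inference and no more.

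A reader might also take 208 steps and 9.4% as the expected harm. The documents do not support that: both figures need consistent steering in all 40 slots and an assumed d of 250.

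**Conclusion.** The concern holds in a limited form. The block size is fixed and disclosed, labelling reads as one code per arm, and concealment of the next allocation is not described. Under sequential assignment with earlier codes visible, 13.3 of 40 codes (33%) are certain and best guesses are right 70.8% of the time, against 3.6 of 40 and 61.6% with one permutation per wave.

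Bias requires more: sequential assignment or freedom over order, sight of the codes by those who schedule or enrol, and a view of which code is blueberry. The exposure is therefore conditional, lies mainly in wave 2 (8.0 of its 24 codes) and in the order of already eligible people, and cannot be sized from the documents. The document does not show that selection bias will occur or that the 0.05 level is lost. The change is still worth making, because it reduces predictability at almost no cost and keeps the 1:1 split within each wave.

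**What to change.** - **Section 4.2, sequence.** Replace the disclosed fixed blocks of 4 with either one random permutation per wave (8:8 and 12:12) or undisclosed, randomly varied block sizes within each wave. If varied blocks are used, choose sizes that add up to 16 and 24, so that each wave still splits in half.
- **Section 3.6, labels.** Replace the single code per arm with participant-level pack numbers. A wave list alone leaves the arm code in place; with unique numbers and a protected list, no allocation can be deduced from labels.
- **List holder and release.** State that the list is held by whoever labels the packets, outside the enrolling team, and that each assignment is released only after final eligibility and baseline data are recorded. Section 3.2 already puts baseline assessments first.
- **Timing.** State whether assignment is by batch or sequential, and bring sections 3.2, 4.2, 5.2 and 5.3 into line.

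Cost: a few sentences, a new list and a little more labelling work, with no extra participants or visits. The downside is slightly looser balance over calendar time within a wave if start dates are staggered.

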## 4.3 Informed Consent

All interested individuals will be asked to provide verbal consent to complete an initial eligibility screen during a phone conversation with study personnel. Potentially eligible participants will then schedule an in-person screening visit. Potential participants may be sent by email or conventional post (per request, and according to their preference) a copy of the informed consent form for them to review at their own pace prior to the in-person screening. Written informed consent will be obtained by study personnel at the beginning of the in-person screening visit.

## 4.4 Participant Withdrawal

Any participant who expresses a desire to discontinue participation in the study will be withdrawn at their request immediately. All data collected prior to withdrawal will be maintained in the study data set.

Additionally, a subject may be withdrawn from the study prior to completing all of the study related procedures due to the following conditions:

- Subject safety issues
- Failure of subject to adhere to protocol requirements (including low compliance with the intervention)
- Disease progression
- Subject decision to withdraw from the study (withdrawal of consent)

Withdrawn subjects may not reenter the study unless there are extenuating circumstances (e.g. family emergency or required travel out of town) that interfere with the start of the study before any medications are administered. In this case, they may be scheduled to start over again. If new medical conditions arise or are exacerbated during the study intervention, the withdrawal of a participant will be evaluated by the PI, SO, and/or study psychiatrist.

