**3-Day Diet Records:** Diet records (consisting of 2 weekdays and 1 weekend day) will be reviewed by research staff for accuracy and completeness. Records will be entered into a dietary analysis program (e.g., Nutrition Data System for Research) to estimate dietary intake of nutrients.

**Height/Weight** will be measured at the baseline visit.

1. Height will be measured using a stadiometer.
2. Weight will be measured using a digital Health-o-meter scale.

**Vital Signs** (e.g., body temperature, pulse, and seated blood pressure) will be measured at the baseline visit. After 3-5 minutes of rest, seated blood pressure will be measured twice with an automated cuff.

**Motives for Physical Activities Measure-Revised (MPAM-R):** Motivation to engage in physical activity will be assessed with the MPAM-R, which is a self-report questionnaire has been used in middle-aged and older adults.

**Blood (up to 10 mL)** will be collected by a trained phlebotomist using sterile procedures. Blood will be processed and stored at -80 degree C for future analyses. Batch analyses of relevant inflammatory markers (e.g., C-reactive protein, interleukin-6, and brain-derived neurotrophic factor) will be measured by a reputable lab (e.g., Quest or collaborators at the University of Connecticut).

**Relevant Symptoms:** Information on relevant symptoms including gastrointestinal distress, appetite, pain etc., will be collected by self-report.

**Compliance:** Compliance with our dietary intervention will be evaluated throughout the study. Participants will be asked to log consumption of their powder and keep all of their used powder packets. At the study visit, participants will return all unused and used powder packets to estimate number of intended doses that were consumed.

**Week 4 Mid-point Visit (~45 minutes):** The Week 4 Mid-point Visit will include an evaluation of motivation, depression level (PHQ-9), suicidal ideation, relevant symptoms and compliance. Participants will again be asked to continue to wear the ActiGraph and provided with new 3-day diet records to fill out the week prior to their next visit.

**Week 6 Mid-point Visit (~45 minutes):** The Week-6 Mid-point Visit will be the same as Week 4 Mid-point Visit, but it will also include turning in diet records, a blood draw of ~10 mL, as well as an evaluation of vitals and social network.

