### 5.3 Dietary Intervention

The duration of this study will be a total of 14 weeks. The first two weeks will require participants to avoid eating certain foods (e.g., fiber- and anthocyanin-rich foods) while also monitoring their usual physical activity with the ActiGraph just prior to the intervention period.

Individuals will then be randomized to either the intervention or the control group. This is a double-blinded study, so the study staff nor the participant will know what powder the participants are assigned to. Those randomized to the intervention group will be asked to consume approximately 48 g of freeze-dried blueberry powder as a source of ~8 g of fiber and 600 mg of anthocyanins. The proposed dose of 48 g of freeze-dried blueberry powder is equivalent to approximately 2 cups of whole blueberries. Individuals randomized to the control group will be asked to consume approximately 48 g of a nutritionally matched placebo powder that is devoid of anthocyanins and fiber.

The powders will be individually packaged in 24 g amounts. Participants will be instructed to consume 2 packets of their respective powder each day for 12 weeks. Participants will be provided with suggestions/recipes on how to consume the powder (for example, mixed in 12 fl oz of water or mixed in 12 fl oz of almond milk). At the beginning of the study the participants will be given a sample of materials (e.g., mixing apparatus) or ingredients (e.g., almond milk) that participants will be able to use to make the suggested recipes they were provided with. It is recommended that participants consume their powder all at once. Given that intervention and control products are regularly consumed, we do not anticipate any toxicities.

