### 5.4 Outcome Measures

Our primary endpoint is engagement in physical activity after 12 weeks of the dietary intervention. Secondary outcomes include feasibility, inflammatory markers, and motivation; however, we will also explore alternative outcomes.

Name	Type	Timeframe	Brief description
Feasibility	Secondary	Throughout the entire study	Participant retention (e.g., the number of participants that complete the intervention out of all participants randomized to an intervention arm)
Inflammatory Markers	Secondary	Baseline, Week 6, and Final Follow-up (Week 12)	C-reactive protein, interleukin-6, and brain derived neurotrophic factor will be measures in blood collected from participants.
Motivation	Secondary	Baseline, Week 4, Week 6, Week 8, and Final Follow-up (Week 12)	Motivation to engage in physical activity will be assessed via self-report questionnaire, Motives for Physical Activities Measure-Revised,
Engagement in Physical Activity	Primary	Baseline, Week 4, Week 6, Week 8, and Final Follow-up (Week 12)	Median daily-step count over the 2 previous weeks.

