## CHAPTER 6. STATISTICAL DESIGN

## **6.1 Statistical Analysis**

All analyses will be performed by intent to treat, and further evaluated per protocol. As a first step, we will assess distribution characteristics of the primary and secondary outcomes. Where appropriate, transformation of variables to combat skew or other irregularities will be employed. Participant characteristics will be summarized using means, medians, standard deviations, interquartile regions and ranges for continuous variables and sample counts and proportions generated for discrete characteristics. Comparability of treatment arms will be assessed on potentially confounding characteristics using tabular and graphical methods.

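### Section 4.4 allows removal from the study, not only from the powder, for low compliance; with no later outcome collection described, such participants would leave the intent-to-treat comparison

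*Combined protocol and SAP*

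**What the plan says.** **Withdrawal.** Section 4.4 states that "a subject may be withdrawn from the study prior to completing all of the study related procedures due to the following conditions". One listed condition is "Failure of subject to adhere to protocol requirements (including low compliance with the intervention"). Re-entry is generally barred. On data, the same section says "All data collected prior to withdrawal will be maintained in the study data set".

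**Compliance.** Section 5.3 sets the intake: "Participants will be instructed to consume 2 packets of their respective powder each day for 12 weeks". Section 5.2 says how it is checked: "participants will return all unused and used powder packets to estimate number of intended doses that were consumed". Neither section says what count is low.

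**Follow-up.** Section 5.2 says "All eligible participants will be asked to continue to wear the ActiGraph for the remainder of the study". Sections 5.1 and 5.2 contain no early-termination visit and no schedule for a participant who is off powder.

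**Endpoint and analysis.** Section 5.4: "Our primary endpoint is engagement in physical activity after 12 weeks of the dietary intervention". Its table also lists step counts at Weeks 4, 6 and 8. Section 6.1: "All analyses will be performed by intent to treat, and further evaluated per protocol". Sections 6.2 and 6.3 specify a change score between baseline and follow-up, compared between arms by Student's t-test. Chapter 6 names no imputation, no repeated-measures model and no sensitivity analysis for missing outcomes. Section 6.4 deals with attrition only by raising 18 per group to 20.

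**Feasibility.** Section 6.2 calls the intervention feasible if at least 80% of those randomised complete the final follow-up.

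**The concern.** Compliance is observed after randomisation. If it can end a participant's outcome collection, the analysis set is shaped by behaviour that the assigned powder may have influenced. Section 6.1 promises a per-protocol evaluation as an addition to intent to treat. Removing poor compliers before Week 12 moves the first analysis toward the second.

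Three results could be affected:

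- the between-arm difference in step change, if those removed differ from those retained and the effect of removing them is unequal across arms;
- the SD of step change, which section 6.4 intends to use in planning later trials;
- the Aim 1 retention result, because each removal is a non-completer created by a staff decision with no stated threshold.

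Outcomes that were never collected cannot be recovered at the analysis stage.

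**Working it through.** **1. Trace one participant through the text.** A participant returns many unused packets. Section 4.4 permits withdrawal from the study before all procedures are done. The request in section 5.2 to wear the ActiGraph runs to the end of the study, so it does not clearly reach someone who has been removed from it. No Week 12 visit is described for that person. The change score in section 6.2 then has no follow-up value, and the t-test in section 6.3 cannot use the record. Medians from Weeks 4, 6 or 8 may exist, but no stated analysis uses them in place of Week 12.

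**2. Reproduce the plan's own figure.** Inputs from section 6.4: SD of change 1,045, difference 1,000 steps/day, alpha 0.05 (two-sided assumed), power 80%.

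n per group = 2 × (1.960 + 0.842)² × 1,045² / 1,000² = 17.1, rounded up to 18. This matches. Raising 18 to 20 implies a loss of 1 − 18/20 = 10%.

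**3. Shift in the arm difference (illustration).** The documents give neither the number removed (k) nor how far their mean change lies from that of those retained (D). Both are assumed here, with all losses in one arm of 20.

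Shift = (k/20) × D. Standard error (SE) = 1,045 × √(1/20 + 1/(20 − k)).

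| k | SE | Shift, D = 250 | Shift/SE | Shift, D = 1,000 | Shift/SE |
|---|---|---|---|---|---|
| 1 | 334.8 | 12.5 | 0.04 | 50 | 0.15 |
| 2 | 339.5 | 25 | 0.07 | 100 | 0.29 |
| 3 | 344.7 | 37.5 | 0.11 | 150 | 0.44 |
| 4 | 350.5 | 50 | 0.14 | 200 | 0.57 |

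With losses in both arms, shift = (k1 × D1 − k2 × D2)/20. This is zero when the two terms are equal or both D are zero. It is 100 steps for two lost per arm with D1 = 1,000 and D2 = 0.

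**4. Effect on the SD (same one-arm assumptions, D = 1,000, equal SD of 1,045 within those retained and those removed).** With p = k/20:

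- Full-arm variance = 1,045² + p(1 − p) × 1,000². This gives an SD of 1,067.5 at p = 0.05 and 1,118.9 at p = 0.20.
- Pooled with the unaffected arm: √[(1,067.5² + 1,045²)/2] = 1,056 and √[(1,118.9² + 1,045²)/2] = 1,083.
- An observed SD of 1,045 would then be about 1.1% to 3.5% too low.
- For comparison, the sampling error of an SD on 38 degrees of freedom is about 1/√(2 × 38) = 11.5%.

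**5. Retention margin.** 80% of 40 is 32, so the criterion tolerates 8 non-completers. Every low-compliance withdrawal uses one of them.

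**The case against.** The strongest reply has five parts.

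- **The rule is discretionary, and this is a pilot.** Section 4.4 says may, its frequency is unknown, and definitive efficacy is left to later trials. This limits the likely size. The plan still specifies a test at p < 0.05 and will carry its SD forward, so the gap remains.
- **Staff are blinded (sections 3.6, 4.6 and 5.3).** They cannot knowingly remove people by arm, which closes the most direct route to imbalance. Compliance could still differ by arm through tolerability: the placebo contains little or no fiber, and section 8.1 accepts that fiber side effects may occur. Section 8.2 does not expect distress if the powder is taken alone, so a difference is possible but not established.
- **Earlier data are kept.** A reader might infer that section 4.4 is silent about the earlier data of participants whom staff withdraw, because the sentence follows the one on withdrawal by request. The wording is unqualified and is naturally read as covering every withdrawal. What is missing is outcome collection afterwards.
- **A threshold may exist elsewhere.** The protocol refers to a manual of procedures, which is not available here. It would be too strong to say that no threshold exists; only that this document states none.
- **Exclusion is not stated.** Section 6.1 declares intent to treat, and using a Week 4, 6 or 8 value is neither specified nor ruled out. The plan does not order these participants to be dropped. Their loss follows from combining the withdrawal rule with a change-score t-test and no missing-data method.

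**Conclusion.** The point stands as a design weakness that should be amended. Section 4.4 permits removal from the study for low compliance, no later outcome collection is described, and the stated analysis cannot include a participant without a Week 12 value.

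The bias cannot be computed. Under the assumptions shown (1 to 4 of 20 lost in one arm, D from 250 to 1,000 steps/day), the shift is 12.5 to 200 steps/day, or about 0.04 to 0.57 SE. The upper end is 20% of the 1,000-step target and requires those removed to differ by the whole target effect. The pooled SD would be at most about 3.5% too low in that range, which is small beside its sampling error. A figure of 2.1% to 6.6% can be derived for the affected arm alone, but it does not describe the pooled SD.

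A reader might conclude that the primary result will be biased. The documents do not support that: there is no effect if the rule is not used, and no bias in the difference if the losses have the same effect in both arms.

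**What to change.** **Section 4.4.** Separate stopping the powder from leaving the study. State that low compliance alone does not end outcome follow-up: unless consent is withdrawn, the participant is asked to keep wearing the ActiGraph and to attend Week 12, and is analysed as randomised. This takes no position on when the powder is stopped.

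**Section 6.1.** Define the per-protocol set by a packet-count threshold fixed before unblinding, as a share of 2 × 7 × 12 = 168 packets.

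**Section 6.2.** Retention is defined there by completing the intervention, but the 80% criterion by completing the final follow-up. Someone off powder who attends Week 12 would meet one and not the other, so state which counts.

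**Section 6.3 (secondary).** State how a missing Week 12 value is handled, whatever the reason for dropout. One option is a repeated-measures model on the step medians already scheduled at Weeks 4, 6, 8 and 12, with one sensitivity analysis. The footnote to the visit table in section 5.1 lets some visits take place by phone without an ActiGraph sync, so some interim medians may be absent.

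**Cost.** A few sentences in an amendment, with no new visits or measurements. The downsides are continued contact with a few participants off powder, some of whom may not wear the device, and a missing-at-random assumption if the repeated-measures model is chosen.
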